Yes. After verifying eligibility and reviewing the consent form during the screening phone call, there is a period of time between the phone call and the enrollment meeting. The length of time between the two varies depending on the meeting time selected by the research participant and team member.

COVID-19 remote modification: after phone screen and verbal review of consent form, e-consent will be emailed within 48 hours. Study will utilize REDCap's auto-email reminder to send up to 3 reminders over the course of two weeks. After that, a team member will follow-up by phone/text/email (potential participant's stated preference of communication) to see if they are still interested in joining the study. For consent forms mailed to the home, similarly timed follow-up will take place by phone (call/text) and/or email.

4. Steps that will be taken to ensure the research participants' understanding:

Study participants will have time to ask questions about the study and review the consent form before signing it.

5. Any process to ensure ongoing consent:

Within approximately one month of the first data collection session, the participants will be made aware of which of the three groups (education/ usual care, resourcefulness, and biofeedback) to which they have been randomly assigned. They will be reminded of remaining study procedures and research staff will answer any questions regarding study procedures or participant concerns as they arise.

6. Steps that will be taken to minimize the possibility of coercion or undue influence to the subjects:

The study participants will be informed that his or her participation in the research study is completely voluntary. If he or she chooses not to participate, it will not affect their current or future relations with the University or with physicians, mental health centers, or community venues from whom they may have obtained information about the study. Study participants will also be informed that there is no penalty of loss of benefits for not participating or discontinuing participation in the study.

For Adult Participants

Indicate if you will be asking for a waiver or alteration of consent process or documentation (consent will not be obtained, written consent will not be documented)

Yes No

If yes, indicate which part of the consent process you are requesting be waived or altered and the rationale for requesting the waiver or alteration:

- I will obtain consent, but not participant's signature

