
Following informed consent, research staff will collect detailed contact information and schedule the first data collection session. The data collection for caregivers sampled involves two structured face-to-face sessions with data collectors. Data will be collected at baseline (T1) and within one month after the 4-week intervention (T2). Measures include dementia symptoms, caregiver reactions, caregiving involvement, dementia knowledge, resourcefulness, heart rate

variability, health risks, and health outcomes, comprising the 156-item questionnaire. Demographic information will also be collected (e.g. occupation, annual income, education, and questions about the care recipient such as age, number of years diagnosed with dementia, specific diagnoses, and questions related to the participant's caring of their family member with dementia). Research assistants will encourage caregivers to respond to items displayed on an iPad/ tablet as they wish, ensuring there are no right or wrong responses. At the first data collection session, the study participant will receive a resource list for Dementia Care support and services in Cuyahoga and surrounding counties.

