Within two weeks of the first data collection session, caregivers will be randomly assigned using a computer program to one of the three interventions (usual care/ education, resourcefulness, or biofeedback). Caregivers will receive the training and perform one health self-management intervention between the T1 and T2 data collections. The education, resourcefulness training, or biofeedback training will be introduced during a single face-to-face session in the caregiver's home/other private venue via a voice-over PowerPoint presentation presented on a tablet. All 90 caregivers who receive an intervention or usual care will keep a written log for the 4-week intervention period between the first (T1) and second (T2) data collection interviews. The caregivers will receive a pamphlet on their intervention (based on the PowerPoint presentation), a tracking log, and will receive telephone, email or text follow-up (preference of the study participant) for the next 28 days while performing the intervention independently and at their convenience. Interventionists will be carefully trained by Drs. [name] and [name] during a 2-day session that will include intervention delivery, cultural diversity training, and methods for providing psychological support/referral (e.g., "first call for help") in case caregivers experience psychological or physical distress during the training session or 28-day intervention period. Interventionists will be blinded to fidelity measures and different interventionists will provide education, resourcefulness training, and biofeedback; they will keep field notes and have weekly supervision by [name].

The first data collection session involves the additional measures of Financial Stress & Resourcefulness, and the second data collection adds an Intervention Evaluation Questionnaire that will ask participants for feedback regarding the intervention they received. Participants randomized to the Resourcefulness Training will be asked to complete the RT Skills Scale as part of the Intervention Evaluation Questionnaire.

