Heart-rate variability (HRV) data will be collected with the Byteflies or a similar HRV device. Once a data collection (T1 or T2) is complete, a team member will make an arrangement to collect HRV data at their home or another agreed-upon location at a set day and time.

- Remote HRV data collection: The participant will receive instructions of how to use the HRV device for a 20-30 minute data collection of HRV; this instruction sheet will also include safety information. The team member will be available to provide support during this time by phone or video call. The data collection may happen at the time of drop-off or sometime that day. There will be a pre-determined time set for pick-up of the device. If need be, this process may be repeated in order to obtain reliable data, and if this data is unable to be collected due to scheduling, it will be considered missing data for that time point.*
- In-Person HRV data collection: Following approved safety plan guidelines (June 2021), a research team member will meet with the study participant to collect the HRV data in person. The data collection will take 10-20 minutes; the entire meeting should be completed within 30 minutes. Like remote data collection, this process may be repeated in order to obtain reliable data (not confirmed until data is analyzed by another team member). Currently enrolled participants will consent to this updated procedure.*

Delivery of the intervention will also be conducted remotely. After randomization, an intervention team member will schedule a 45-minute video call to present the intervention. This meeting will include a power point presentation, a review of the online tracking log, and instructions for the 28-day intervention period. An electronic copy of the corresponding

the study participant.

Gift cards will replace in-person cash compensation throughout the study period.

Study Timeline (optional)

ClinicalTrials.gov Information

Directions: If this study has been registered on ClinicalTrials.gov, provide the ClinicalTrials.gov identifier and the investigator/sponsor responsible for registering. If this study has not been registered on ClinicalTrials.gov, provide the rationale as to why and if/when it will be. If it does not meet the requirement for being registered on ClinicalTrials.gov, please state that.

NCT04247347 [name]

List of Data to be Collected

- *Indicate what identifiers you will collect*

- Name

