- There will **not** be a formal Data and Safety Monitoring Board/Committee.

There will be a formal Data and Safety Monitoring Board/Committee. Provide information about the DSMB/C including the contact information of the committee member(s) (as applicable); whether it is independent from the study sponsor; how often it meets; the type of data that will be used; written reports, etc.

A Safety Monitoring Committee (SMC) has been formed as the monitoring entity for this grant. The SMC is independent from the study sponsor and consists of:

- *[name] , SMC chair, who serves as the Associate Dean for Research and is Associate Professor, Frances Payne Bolton School of Nursing, CWRU
[contact]*
- *[name], Assistant Dean for Research, and Professor, Frances Payne Bolton School of Nursing, CWRU
[contact]*
- *[name], Professor of Psychiatry from the CWRU School of Medicine,
[contact]*
- *Study team members will include [name], PI, and [name], statistician [contact]*

1. Monitoring Study Safety

- a) Monitoring schedule - Twice per year throughout the project, the SMC will review data on the study regarding study safety. For example, the SMC will review any occurrences of caregiver emotional distress that required intervention by data collector or interventionist as well as those requiring referral and follow-up and instances where caregivers withdrew from the study.*
- b) Audits for compliance with IRB requirements – Random internal audits of 10% of the files will be done twice annually to insure the approved IRB protocol is being followed. The SMC will review recruitment procedures, compliance with meeting the inclusion/exclusion criteria, consistency with random assignment process to the treatment conditions, provision of interventions within timeframe defined within the protocol, and scheduling of data collection sessions as outlined within the protocol.*
- c) Conformance with informed consent requirements – Random internal audits will be conducted twice per year to verify that informed consent requirements are being met. For example, the SMC will review 10% of the consent forms for signatures and dates, make sure all consent forms are accounted for and stored in locked files and that the correct form is being used. Data collectors will be asked to describe the consent process quarterly to re-assess their knowledge of this process quarterly and review / retraining will be done as needed.*

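### Assignment can precede disclosure and training by weeks, and T2 is dated only from the intervention's end, so a caregiver allocated but never trained has no T2 date and is lost to Aim 1

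*Combined protocol and SAP*

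**What the plan says.** Four timing statements bear on this point.

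- **Assignment** (Study Design/Procedures): "Within two weeks of the first data collection session, caregivers will be randomly assigned using a computer program to one of the three interventions".
- **Disclosure** (Consent Process, item 5): "Within approximately one month of the first data collection session, the participants will be made aware of which of the three groups" they have been assigned to.
- **Training** (Study Design/Procedures): "Caregivers will receive the training and perform one health self-management intervention between the T1 and T2 data collections". Under the COVID-19 remote modification: "After randomization, an intervention team member will schedule a 45-minute video call to present the intervention". Neither statement gives a limit in days. Practice then runs "for the next 28 days while performing the intervention independently and at their convenience".
- **T2** (Study Design/Procedures): "Data will be collected at baseline (T1) and within one month after the 4-week intervention (T2". The Objectives also place the follow-up measurement within a month of the intervention. Neither place counts it from T1 or from assignment.

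Three further statements matter. On staffing, "different interventionists will provide education, resourcefulness training, and biofeedback". In the section on monitoring data for participant safety, item b has the safety committee audit "provision of interventions within timeframe defined within the protocol". Under Withdrawal of Research Participants, people who stop responding are withdrawn, and nothing more is collected from anyone after withdrawal.

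The Data Analysis Plan specifies a three-group by two-wave RMANOVA for Aim 1. It names no analysis population, gives no rule for a missing T2 and makes no use of elapsed time.

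**The concern.** Randomisation fixes who must be counted in the comparison. Here the assignment may exist for some weeks before the caregiver hears of it or is trained. Anyone who goes silent in that gap is already randomised. Because T2 is defined only from the end of an intervention, a caregiver who never starts one has no date on which T2 is due. A conventional two-wave RMANOVA uses only people with both waves, so that caregiver disappears from the primary analysis. The plan has no rule that would bring the caregiver back.

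There is a secondary issue. Each arm has its own interventionists, who book training after assignment, so the wait could differ by arm. The analysis treats T1 and T2 as wave labels, so a difference in elapsed time between arms would be absorbed into the time-by-group term. The committee's audit of delivery timing cannot settle the matter as written, because no section sets the timeframe it is meant to check.

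**Working it through.** **Inputs.** Assignment: day 0 to 14 after T1 (Study Design/Procedures). Disclosure: up to about day 30 (Consent Process, item 5; one month taken as 30 days). Training: no limit. Intervention: 28 days. T2: 0 to about 30 days after the intervention ends. Target: 100 caregivers from 125 screened, with about 20% ineligible (Number of Research Participants).

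**The plan's own figure.** 100 / (1 − 0.20) = 125, which reproduces. The allowance covers ineligibility at screening only; nothing is stated for loss after assignment.

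**Gap from assignment to disclosure.** The outer limits are 30 − 14 = 16 days apart. The longest gap within the limits is 30 − 0 = 30 days, and the shortest is zero.

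**T1-T2 span.** Span = w + 28 + v, where w is the wait from T1 to training and v (0 to 30) is the delay from the end of the intervention to T2.

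| Training on day | Earliest T2 | Latest T2 |
|---|---|---|
| 0 | 0 + 28 + 0 = 28 | 0 + 28 + 30 = 58 |
| 14 (assignment limit) | 14 + 28 + 0 = 42 | 14 + 28 + 30 = 72 |
| 30 (disclosure limit) | 30 + 28 + 0 = 58 | 30 + 28 + 30 = 88 |

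The full range is 28 to about 88 days, a ratio of 88 / 28 = 3.1. Of the 60-day spread, 30 days come from w and 30 from the T2 window. Training after day 30 adds a day for each day of delay, with no stated ceiling.

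**A caregiver never trained.** Here w does not exist, so the span, and with it the T2 date, is undefined.

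**Number lost.** Each 1% of 100 allocated caregivers who are never trained is 1 person. The documents give no rate. An assumed 3% to 10% would be 3 to 10 caregivers.

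**Bias from unequal waits.** To a first approximation, bias = (difference between arms in mean wait) × (outcome drift per unit time). Neither factor is in the documents. If the first is zero, the bias is zero however wide the spread of spans.

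**Would one allocation-based T2 date for everyone work?** A caregiver assigned on day 0 and trained on day 30 finishes on day 30 + 28 = 58. Any common date earlier than 58 days after assignment would fall before that caregiver had completed the 28 days.

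**The case against.** The strongest reply is that nothing here contradicts anything else. Two weeks and one month are both upper limits, disclosure may follow assignment at once, and no section says the assignment is withheld. Every window is the same in all arms, and a span that varies equally in all arms adds noise, not confounding. Half of the 60-day spread is the T2 window. Counting T2 from the end of the intervention is also a reasonable choice, because it ensures measurement after the full 28 days. All of this stands.

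Caregivers lost before disclosure do not know their arm, so knowledge of arm cannot drive that loss. This also stands, but only up to disclosure. Between disclosure and training the caregiver does know, and the committee is itself asked to review refusals of interventions.

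A new T2 date will not recover someone who cannot be reached or has withdrawn. That is true, and it is why the timing of assignment matters more than the T2 date. The committee also audits assignment, delivery and scheduling twice a year and monitors attrition by group. That can reveal a problem, but it supplies neither a delivery limit nor an analysis rule.

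Three stronger readings are tempting and are not supported:

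- **That waits will differ by arm.** Separate interventionists make this possible; nothing shows it.
- **That the caregivers are declining fast enough for a few weeks to matter.** The worsening course in the Background is that of the dementia. For caregivers it says only that stress may harm health over time, with no rate. An assumed drift of 0.02 to 0.05 SD per week with arm waits 1 to 3 weeks apart would give 0.02 to 0.15 SD, but 52 weeks at that drift is 1.0 to 2.6 SD a year, which is hard to credit over a caregiving career the Background puts at 4 to 20 years.
- **That the 90 caregivers mentioned in Study Design/Procedures, against a target of 100, show loss before treatment.** The figures would fit that, but the documents do not explain the difference.

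**Conclusion.** The point holds as an avoidable design gap. It is not a contradiction and not a demonstrated bias. The plan permits up to about 30 days between assignment and disclosure, sets no limit on training, and gives no T2 date to anyone who is assigned but not trained. Such caregivers leave the Aim 1 RMANOVA after randomisation.

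By the stated limits, and taking a month as 30 days, the wait before training contributes 0 to about 30 days to the T1-T2 span, provided training comes no later than the disclosure limit. The number of caregivers affected and the size of any bias cannot be derived from the documents. The case for change rests on how easily these exclusions can be prevented, not on a calculated effect. The absent training limit and the lack of interval reporting would, on their own, be missing detail.

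**What to change.** 1. Run the computer assignment only when the caregiver has been reached and can be told the arm and booked for training in the same contact. Most people who go silent would then be lost before randomisation, where they do not affect the comparison.
2. Seek T2 from every allocated caregiver who has not withdrawn. Keep the current window after the 28 days for those trained. For those not trained, use a pre-set date counted from assignment, the same in all arms.
3. State in the Data Analysis Plan that all allocated caregivers are analysed by assigned arm, with a rule for a missing T2. A mixed model with the same group and time terms is one way to keep those with T1 only.
4. State one T1-to-training limit so that Consent Process item 5, Study Design/Procedures and the committee's timing audit agree.
5. Report T1-to-training and T1-to-T2 intervals by arm.

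The cost is protocol wording, a change in when the assignment is run, and T2 sessions for caregivers who now have none scheduled. No additional caregivers are needed. Staff must reach the caregiver before assigning. Because caregivers are already enrolled, item 1 can apply only to those not yet allocated; items 3 and 5 can cover everyone.

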| 2. Has not cared for a living family member for at least the last 6 months. |
| 3. Has knowledge of another family member in the same household enrolled in the study |
| 4. Currently pregnant |
| 5. Has a pacemaker |
| 6. Lives outside of the study area |

Number of Research Participants

Directions: Indicate the target number of research participants to be accrued locally, and, if this is a multi-site study, indicate the total number of research participants to be accrued across all sites.

Based on previous research by the PI and Co-Is, we conservatively estimate that ~20% of caregivers may not meet eligibility criteria. Thus, we will screen 125 participants to obtain the desired sample of size of 100.

Special/Vulnerable Populations

1. Indicate specifically if you will include each of the following special populations by checking the appropriate box:

- Adults unable to consent**
- Minors (infants, children, teenagers)**
- Wards of the state
- Foster Children
- Pregnant Women
- Neonates
- Neonates of Uncertain Viability
- Employees of CWRU or UHHS
- Prisoners
- Illiterate Individuals
- Non-English Speaking
- University Students

None

2. If the research involves individuals that are included in a special/vulnerable population, describe the additional safeguards included to protect the rights and welfare of the individuals for each population indicated.

If family caregivers who do not speak/understand the English language come forward with interest in participating and if they meet all other study criteria, we will make accommodations for translating the study measures and intervention materials or for having an interpreter provide appropriate explanations. If an illiterate individual comes forward with interest in participating and if they meet all other study criteria, we will make accommodations to dictate the consent form and all study questions. If a caregiver is an employee or student of CWRU, the consent form identifies participation in this research study as voluntary and if they choose not to participate, it will not affect their current or future relations with the university. No caregivers unable to consent will be enrolled. Adults unable to consent are only subjects to the extent that there is any identifiable information about them collected through the caregiver. They will not be present for any interventions or interactions.

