3. If excluding pregnant women, illiterate or non-English speaking individuals, provide a scientific rationale for the exclusion. Inconvenience or cost is not an acceptable rationale.

Pregnant women are excluded due to the measure of heart rate variability (HRV). The inclusion of pregnant women has the potential to alter the analyses that involve HRV measurement.

Recruitment Methods

Note: Attach all applicable recruitment materials to the last section of the Smart form under “Recruitment Materials.”

1. Which of the following methods will be used to recruit research participants. [Select all that apply](#)

- Email
- Phone call
- Letter
- Advertisement (e.g., poster, flyer, etc.)
- Social media
- Other. Please specify:

2. Describe when, where, and how potential research participants will be recruited.

The 100 family caregivers will be recruited from Cuyahoga County and 6 adjacent counties through social service advocacy agencies, community agencies, dementia care day programs and care facilities, and private physicians' offices who agree to provide us with access for posting / distributing information about the study. Agency personnel may assist us in identifying potential study participants who meet the following inclusion

criteria: caregivers will be at least 18 years old, report having a family member with dementia, and providing care or support for them for at least 6 months, but not necessarily in the same household (i.e. they may be living in a dementia care facility). However, we anticipate that most of the potential study participants will be those who see a posted advertisement or receive a flyer describing the study from one of agencies, centers, dementia care facilities, offices, etc., where we have permission to post / distribute information about the study. Contact information for the research office will be included on the flyers. Potential study participants will contact the research office for screening by a research team member to ensure he/she meets the eligibility criteria. If eligible, the team member will obtain their name, contact information (phone and/or email), address, and time / best method for the data collector to call to make an appointment to meet to discuss and enroll in the study, obtain their informed consent to participate, and conduct their first data collection interview.

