member will then confirm and enter contact information in REDCap, as well as update the Box Screening and Enrollment Log; this includes the individual's full name, mailing address, phone number(s), email address, best time of day to call, and confirming if the study team can leave voice mail messages, text to schedule / confirm study visits and intervention check-ins, and/or send mail to their mailing address if we are having trouble contacting them by phone or email

5. Describe the feasibility of recruiting the required number of suitable research participants within the agreed recruitment period. For example, how many potential research participants do you have access to?

Based on previous research by the PI, we conservatively estimate that 20% caregivers may not meet eligibility criteria. Thus, we will screen 125 potential participants to obtain the desired sample size of 100.

Setting

Directions: Make sure to describe: 1) sites and locations where your research team will conduct the research; 2) where your research team will identify and recruit potential research participants; and 3) include the physical location where research procedures will be performed.

The project manager or other research team member will screen by phone to determine eligibility and schedule first data collection meeting. All data will be collected either in the community (e.g. participants home or other private venue of their choice, including mental health center/physician's office, private/ closed room in local library, etc.), on the campus of Case Western Reserve University (e.g. the School of Nursing).

Study participants (who meet the study criteria) will be recruited through both public and private advocacy agencies, care facilities, support groups, community health centers, health fairs and other community events, print and e-newsletters (e.g. CASE Daily), listservs, local magazines and newspapers, ResearchMatch.com, Alzheimer's Association TrialMatch, and private physician offices in Cuyahoga and 6 adjacent counties in Northeastern Ohio.

Consent Process

Indicate whether you will be obtaining consent:

Yes No

If yes, answer the following questions:

1. Describe where the consent process will take place:

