Before the T1 interview, the data collector will obtain the caregiver's written informed consent to participate. All research staff (including the project manager, data collectors, and interventionists) will be required to complete the "human subjects" training and obtain certification prior to entering the field for data collection or intervention. The consent form will explain the expectations of caregivers as research participants, risks they may encounter, benefits they may accrue, measures to be taken to maintain confidentiality, and voluntary nature of their participation. Potential study participants will be told they are being asked to participate in a study to examine method for helping family caregivers to self-manage their health. They will be told that they will be randomly assigned (using a computerized system) to one of the three treatment conditions. They will be told the study involves 2 face-to-face interviews with a trained data collector during which objective, validated questionnaires and HRV measures will be completed, as well as an intervention ("stress management method") between the first and second data collection interviews. The caregivers will be told that their confidentiality will be protected and that their names will not be revealed; results of the study will be reported in aggregate. They will be told that they are free to withdraw from the study at any point in time and that they do not need to supply responses to all questions posed on the study questionnaires. They will be told about the possible risk of feeling distressed while answering questionnaires or completing their daily logs, or using the biofeedback device (if applicable) and about measures that will be taken to minimize / manage the distress, including discontinuing participation and referral to mental health professionals if needed. They will be told that if a research team member, during a data collection or intervention meeting or call, suspects or witnesses any signs of elder abuse, neglect, or exploitation, a report will be filed with the county department of job and family services in compliance with Ohio law. They will be told about the potential benefit of stress reduction. Finally, they will be told that they will receive an incentive of \$20 at T1 and \$25 at T2. In addition, they will receive \$20 for completing the face-to-face intervention session and \$5 for each week of completion of the progress log (up to 4 weeks or \$20). Participants will receive up to \$85 for completing all study activities.

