- d) Verification of source documents – This study does not involve printed or written documents; data will be collected through electronic data capture using REDcap software and then downloaded directly into SPSSPC files. Heart rate variability data will be downloaded from the assessment device and transcribed into the SPSSPC files. These sources will not include any data that would be personally identifiable.*

The SMC will review 1) all causes of mortality (e.g., caregiver death); 2) issues with participation (e.g., numbers and reasons for withdrawing from the study or refusing interventions, etc.) as well as recruitment refusal (percent and reasons) and subject attrition (percent and reasons); 3) missing data (including whether there are systematic patterns or whether data are missing at random); and 4) errors in data entry (which are expected to be minimal given the use of software for data collection with direct download into SPSS). In addition, differential attrition from the intervention groups (including the control and usual care groups, and the groups assigned to intervention based on need or personal preferences) will be monitored.

If concerns or problems are identified by the SMC, they will be reported to the IRB and NINR/NIH via email by [name] and [name], respectively, within 3 business days after they are identified. If there are recommendations made by the SMC, the action plan for response or notice of any actions taken by the IRB regarding the research and any responses to those actions will be provided to NINR Officials within 2 weeks.

e) Investigator compliance – Compliance of the investigators and all research team members who will have access to the data will be monitored annually. All research team members will be CREC certified; the CWRU intranet hosts a website where verification of compliance with continuing education for all investigators and team members can be evaluated.

2.) Reviewing and Reporting Adverse Events/unanticipated problems

1. Event identification

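### Does the count of 90 treated caregivers contradict the target of 100, and is screening 125 too few to reach it?

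*Combined protocol and SAP*

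**What the plan says.** The target appears three times and is consistent. Number of Research Participants states: "Thus, we will screen 125 participants to obtain the desired sample of size of 100". Recruitment Methods, item 2, begins: "The 100 family caregivers will be recruited from Cuyahoga County and 6 adjacent counties". Item 5 of the same section repeats: "Thus, we will screen 125 potential participants to obtain the desired sample size of 100". Both screening statements rest on about 20% of caregivers being ineligible, an estimate the protocol calls conservative.

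Study Design/Procedures says of participants that "they will be randomly assigned (using a computerized system) to one of the three treatment conditions". The conditions are education (usual care), resourcefulness training and biofeedback, so there is no untreated group. The same section then gives a different count when it describes the logs: "All 90 caregivers who receive an intervention or usual care will keep a written log for the 4-week intervention period".

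Consent and the T1 interview come first, randomisation follows up to two weeks later, and the training session comes after that. Withdrawal of Research Participants allows people to leave at any time. The safety-monitoring section has the committee look at refusals, attrition and refused interventions. No section gives an expected rate for any of these.

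**The concern.** A design with 100 recruits, all randomised to a treated or usual-care arm, should have 100 people keeping logs unless some are lost first. The protocol gives 90 as a flat count and offers no loss rate that leads from 100 to 90. A reader could take 90 as the number treated, the number completing, or a different target of 30 per arm. With no power analysis in the Data Analysis Plan, these counts are the only guide to the planned precision of Aim 1.

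The screening figure raises a second doubt. The entire gap between 125 and 100 goes to ineligibility. Yet Consent Process, item 3, expects some eligible people to hesitate: it provides for up to three reminders and then a contact "to see if they are still interested in joining the study". If some decline, 125 screened would yield fewer than 100 at the planned ineligibility rate.

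**Working it through.** **Inputs from the protocol.** Target 100; screened 125; ineligible about 20%; caregivers keeping logs 90; three arms. The allocation ratio, refusal rate, attrition rate, alpha, power, effect size and T1–T2 correlation are not given. Values used for these below are assumptions.

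**The plan's own figure.** Number to screen = N/(1 − ineligible) = 100/(1 − 0.20) = 125. In reverse, 125 × 0.80 = 100. The stated figure reproduces exactly.

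**Adding refusal.** Enrolled = 125 × 0.80 × (1 − r), where r is the assumed share of eligible caregivers who decline:

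| Assumed r | Enrolled from 125 | Screened to reach 100 |
|---|---|---|
| 0 | 100 | 125 |
| 5% | 95 | 132 |
| 10% | 90 | 139 |
| 20% | 80 | 157 |

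**If 20% really is conservative.** Refusal that can be absorbed = 1 − 100/[125 × (1 − i)], where i is true ineligibility. At i = 15%, 1 − 100/106.25 = 5.9%. At i = 10%, 1 − 100/112.5 = 11.1%. So some refusal fits within 125 if ineligibility turns out lower than planned, and none fits if it is exactly 20%. The text does not forbid screening more.

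**100 against 90.** The gap is 10, or 1 − 90/100 = 10%. Losses of that size between T1 and the training session would produce 90 from 100. So would a leftover target of 3 × 30. The documents do not decide between these readings.

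**Effect on precision.** Standard-error ratio = √(100/90) = 1.054. For a change-score comparison of one arm with education, I assumed equal arms, 80% power and a two-sided 5% level, with SD factor √(2(1 − ρ)) and a noncentral t on 3n − 3 degrees of freedom. The detectable difference, in SD units, is:

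| Assumed ρ | n = 33 per arm | n = 30 per arm |
|---|---|---|
| 0.6 | 0.623 | 0.654 |
| 0.5 | 0.697 | 0.731 |

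The change is about 0.03 SD in either row.

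**Where the numbers are used.** The Data Analysis Plan specifies a three-group by two-wave repeated measures ANOVA for Aim 1, two-by-two versions for Aim 2, and chi-square tests for Aim 3. None of these refers to 100 or 90.

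**The case for a change.** The strongest case for a change is that a core design number appears in two versions and the text does not reconcile them. If 90 caregivers were treated, a reader could not say from Study Design/Procedures whether the plan had been met or a tenth of the sample lost. The monitoring section adds to the doubt, because its list of groups for differential attrition includes a control group separate from usual care and groups assigned by need or preference. The three-arm design has none of these, so someone might suppose that 10 caregivers receive neither an intervention nor usual care. The remedy would cost only a few words.

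Part of this stands. Both numbers are in the current text, the 90 is unexplained, and no fourth arm accounts for the difference. The rest does not carry the point. The accrual target is not in doubt, since three statements agree on 100, so 90 treated would be read against 100 recruited. The 90 is limited to those who receive an intervention or usual care. That group can be smaller than the group recruited, because consent and T1 precede randomisation and training. The monitoring committee reviews refusal and attrition as percentages with reasons. These come from observed counts, and no threshold is tied to a planned 100 or 90. Whether the protocol should contain a power analysis is a separate question.

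**Conclusion.** No change follows. The 90 is either a clerical leftover or an unlabelled expected number of treated caregivers, and it stands in a sentence about log-keeping that drives nothing else. The screening figure is arithmetically correct. Asking for a separate refusal rate would add planning detail without correcting an error, and a shortfall can be met by screening more people. As written, the plan leads the sponsor to aim for 100, randomise all who remain, and apply the same analyses whichever number the log sentence gives. Reported counts at each stage will show who was enrolled, randomised, treated and measured at T2.

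If the number analysed were 90 instead of 100, the cost would be a standard error about 5.4% larger and a detectable difference about 0.03 SD larger. The second figure rests on the assumed allocation, correlation, power and significance level. The enrolment shortfalls in the refusal table depend entirely on assumed refusal rates and on ineligibility of exactly 20%.
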